## **5.2 Confidentiality of data**

Every effort will be made to protect subject confidentiality. Subject names and personal identifiers will not appear in any publications resulting from this work. Subjects will be informed that the sponsor, the IRB, and regulatory authorities will have access to records that identify them as individuals. All applicable Health Insurance Portability and Accountability Act (HIPAA) regulations will be followed.

## **5.3 Data Processing**

SPR Therapeutics, LLC, or its designated Contract Research Organization (CRO), will be responsible for database creation, double data entry, generation of database queries, and data analysis.

All CRFs will be monitored by SPR Therapeutics personnel (or their authorized representatives). Completed, monitored forms will be returned to SPR Therapeutics for entry into the database. Visual checks will be completed for generation of site queries. The Investigational Site will be queried for missing data, inconsistent data, or illegible information via Query Forms. Following site query resolution, all Query Forms will be returned to SPR Therapeutics for inclusion into and/or modification of the study database.

## **5.4 Data Analysis**

All primary and secondary endpoint data will be analyzed and reported. This study is a non-randomized case series involving up to 45 SPR Trial Stage and approximately 18 SPR Implant Stage subjects.

### **5.4.1 Primary Efficacy Endpoint Analysis**

Within subject analyses of the primary endpoint, the BPI3, are performed for each subject throughout the study. First, the BPI3 is collected and analyzed at the end of the sham period during the SPR Trial Stage, to evaluate the placebo effect. Second, the BPI3 is collected at the conclusion of the SPR Trial Stage to determine the proportion of subjects who experienced clinically significant pain relief during the Trial Stage (i.e., Trial Stage Success proportion). Third, the BPI3 is collected during the Trial Stage Follow-up period to assess the return of pain and determine if a subject is eligible to advance to the SPR Implant Stage. Finally, the BPI3 is collected and analyzed during the SPR Implant Stage to determine the success of the SPR Implant System for the individual.

A subject will be considered a Trial Stage Success if he/she achieves at least a 2-point reduction in post-stroke shoulder pain intensity score in the BPI Pain Intensity Question #3 (BPI3) at the end of the Trial Stage (Visit 5) relative to end

of the placebo period or baseline (Visit 4 or Visit 1), whichever is lower OR reports a BPI3 score of zero at the end of the Trial Stage.

A subject will be considered an Implant Stage success if he/she achieves at least a 2-point reduction in post-stroke shoulder pain intensity score in the BPI Pain Intensity Question #3 (BPI3) at the 12-week post-IPG stim on visit (Visit 10) relative to end of the placebo period or baseline (Visit 4 or Visit 1), whichever is lower OR reports a BPI3 score of zero at the 12-week post-IPG stim on visit.

A description of each analysis is presented below and details regarding the statistical methods are presented in Section 6.

#### **5.4.1.1 Determination of Placebo Effect During SPR Trial Stage**

For each subject, a within subject analysis will be performed to evaluate if a placebo effect occurred during the sham stimulation period. The BPI3 score collected at the End of the sham period (Visit 4) will be compared to the BPI3 score collected at Baseline (Visit 1).

If

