## 4.2 Study Population

### 4.2.1 Selection Criteria

Subjects will be screened for eligibility from the available pool of candidates with post-stroke shoulder pain seen by the Investigator. The specific inclusion and exclusion criteria are listed in **Table 2** below. The total number of subjects and sites we are requesting for this study are listed immediately following the Inclusion/Exclusion Criteria and are presented in **Table 3**.

**Table 2.** Inclusion/Exclusion Criteria

Inclusion criteria	Exclusion criteria

At least 21 years old

≥6 months after the stroke that caused shoulder pain

Subject failed or did not tolerate at least two conservative therapies for a total period of at least 6 months since the onset of post-stroke shoulder pain.

Shoulder pain as indicated by a score of ≥4 on the Brief Pain Inventory (BPI3)

Upper extremity hemiplegia (No shoulder abduction, shoulder abduction in synergy or if

	

Evidence of joint or overlying skin infection of the affected limb

Taking any opioid medication (or Tramadol) for shoulder pain OR for any other chronic pain condition

Intra-articular or sub-acromial steroid injections or botulinum toxin injections to the affected shoulder in the previous 12 weeks

History of arrhythmia with hemodynamic instability, such as ventricular tachycardia, supraventricular tachycardia and rapid ventricular response atrial fibrillation OR valvular heart disease including artificial valves

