--	---

We are requesting the following number of subjects and sites for our Pilot Study (**Table 3**).

**Table 3.** Subject and Site Totals Requested for Pilot Study

Description	Number of Subjects/Sites
-------------	--------------------------

Total Number of Subjects enrolled for eligibility (evaluation of minimum pain score on BPI3 inclusion criterion; INR testing in selected individuals, and pregnancy test)	Approximately 90
Total Number of Subjects undergoing SPR Trial Stage (Smartpatch System)	Up to 45
Total Number of Subjects with SPR Implant Stage (implantation of IPG and Implantable Lead)	Approximately 18
Number of Pilot Stage Investigational Sites	Up to 5 sites

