#### **4.5.1 Baseline (Visit 1)**

Potential study participants will be screened for eligibility from a pool of candidates with post-stroke shoulder pain and recorded in the Subject Screening Log. Patients meeting all general eligibility criteria will be asked if they are interested in participating in the study. The Informed Consent Form will be reviewed with the potential subject to ensure that the risks and benefits of study participation are fully understood. The Informed Consent for this study consists of two documents: the Trial Stage Consent Form and the Implant Stage Consent Form. Prior to any data collection, subjects who agree to participate in the study must sign the Trial Stage Informed Consent Form and will be asked to read the Implant Stage Consent Form such that the risks of participating in both phases of the study are presented to the subject. The Trial Stage Informed Consent Form may be signed up to 30 days prior to the SPR Trial Stage procedure. Prior to the Implant Stage procedure, the study participants who qualify to progress onto the Implant Stage (and agree to continue to the Implant Stage) will be asked to review and sign the Implant Stage Consent Form such that the risks of participating in that phase of the study are clearly understood.

Subjects will then be screened for their cognitive ability to participate in the study and complete the required surveys. The Mini Mental Status Exam (MMSE) will be administered to determine the subject's cognitive ability to participate in the study. The MMSE has been validated as a cognitive function survey instrument and has been widely used in stroke patients. Subjects must score  $\geq 24$  on the MMSE in order to qualify. [REDACTED]

[REDACTED] The Investigator will also determine their ability to rank pain based on interactions during the screening process or prior medical interaction with the subject.

Subjects will then be given the Brief Pain Inventory Short Form to determine their baseline degree of pain. Subjects will be instructed to focus on their shoulder pain when answering the BPI and must rate their worst pain in the last week as  $\geq 4$  on the BPI3 numeric rating scale to qualify for the study.

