#### **4.5.2 SPR Trial Stage**

##### **4.5.2.1 SPR Trial Stage Procedure/Start of sham period (Visit 2)**

Following the baseline visit, subjects will return to the clinic for the SPR Trial Stage Procedure. During the SPR Trial Stage procedure, a Smartpatch Lead will be placed. At the conclusion of this visit, the sham period will begin for each subject.

To determine a suitable location for placement of the Smartpatch Lead, [REDACTED]

[REDACTED]

[REDACTED]

Prior to leaving the clinic, subjects and their caregivers will be instructed on the proper care of the percutaneous lead exit site. To initiate the 3-week sham period, the Smartpatch Stimulator and Smartpatch Pad will be connected to the Smartpatch Lead (via the Smartpatch Lead Connector). The Investigator will then program the stimulator to deliver sham stimulation (i.e., no stimulation), which is further described in the SPR Clinician Manual. [REDACTED]

The subject will be instructed on how to turn stimulation on/off and how to connect and disconnect the Smartpatch Stimulator, Smartpatch Pad, Smartpatch Cable, Lead Connector Tapes, and adhesive bandages. The subjects will be instructed to use the Smartpatch Stimulator for a total of 6 hours each day.

Subjects will be blinded to this sham period

Subjects will also be instructed that they may or may not feel some of the stimulation levels.

Data regarding the specific details of the SPR Trial Stage procedure will be collected during this visit. In addition, the SPR Trial Stage procedure may be video taped for educational and training purposes. Subject faces will not appear in the video and each subject will sign a separate video consent (if applicable at the Investigational Site) if they agree to be video taped.

A detailed description of the SPR Trial Stage procedure and programming instructions, including instructions for Sham Programming Mode, for the Smartpatch System is provided in the Clinician Manual.

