**$P_0$  = BPI pain score at Baseline**

**$P_1$  = BPI pain score at End of Sham**

Then, a positive placebo effect is present in any subject who has a decrease in their BPI3 score from Baseline to the End of Sham:

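### The sham (placebo) effect is measured from the same Visit 1 BPI3 that had to be 4 or more to qualify, so regression to the mean and any drift before lead placement are counted as placebo effect

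*Combined protocol and SAP*

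**What the plan says.** Table 2 sets the entry rule: "Shoulder pain as indicated by a score of ≥4 on the Brief Pain Inventory (BPI3"). Section 4.5.1 collects that score at Visit 1 and uses it as baseline too: "Subjects will then be given the Brief Pain Inventory Short Form to determine their baseline degree of pain". In Section 5.4.1.1 it becomes P0: the Visit 4 score, P1, "will be compared to the BPI3 score collected at Baseline (Visit 1"), and "a positive placebo effect is present in any subject who has a decrease in their BPI3 score from Baseline to the End of Sham". No minimum size of fall is required.

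On timing, Section 4.5.1 has consent come first ("Prior to any data collection, subjects who agree to participate in the study must sign the Trial Stage Informed Consent Form") and adds: "The Trial Stage Informed Consent Form may be signed up to 30 days prior to the SPR Trial Stage procedure". Placement is a separate visit: "Following the baseline visit, subjects will return to the clinic for the SPR Trial Stage Procedure". The readable Visit 2 text in Section 4.5.2.1 mentions no BPI3. The list of key BPI3 evaluations in Section 4.4.1.1 starts at Visit 4, and Section 4.1 has endpoints assessed at baseline and next at the end of sham.

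Section 6.1.2.1 compares the proportion of successes at the end of sham with that at the end of the Trial Stage, and applies a Wilcoxon signed rank test to the change in BPI3. Trial Stage success (Sections 4.1 and 5.4.1) needs a 2-point reduction from the lower of Visit 1 and Visit 4, or a score of zero at Visit 5.

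**The concern.** A score used to select subjects is a biased starting point for measuring their change. Those let in by a chance high reading will on average score lower next time, with or without a device. The single-arm, fixed-sequence design has no concurrent group to show how large that fall is, and no second pre-device score is described.

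Evaluating the placebo effect is a stated aim (Section 1.5), and the study is meant to inform a larger pivotal trial. If regression to the mean is reported as placebo effect, the sponsor carries an overstated sham response into that design, and the comparison in Section 6.1.2.1 is tilted against the device.

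**Working it through.** **The plan's own figure.** There is none to reproduce. The power inputs in Section 4.3.1 are redacted, and no expected sham effect is given.

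**Inputs from the documents.** Cut-off of 4 on a 0-10 scale; sham period of 3 weeks; up to 45 treated from about 90 evaluated (Table 3).

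**Assumptions, not in the documents.** SD of BPI3 among candidates 2.0-2.5; test-retest correlation r of 0.6-0.8; share of candidates passing the cut-off 50%, 79% or 90%. The 79% is borrowed from the first-stroke cohort in Section 2.2.1, where about 79% of patients with shoulder pain scored 40-100 on a 100-point scale. That is another instrument and population, so it is only illustrative.

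**Model.** A stable true score plus independent error at each visit, rounded and clipped to 0-10; subjects kept if Visit 1 is 4 or more; no placebo effect, drift or stimulation effect. At least 1,000,000 simulated subjects per scenario.

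**Mean spurious fall, Visit 1 to Visit 4**

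| Share passing | Mean fall (points) |
|---|---|
| 90% | 0.09-0.20 |
| 79% | 0.16-0.37 |
| 50% | 0.35-0.81 |

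From a Visit 2 score that played no part in selection, the mean fall is 0.00 in every scenario.

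**Analytic check at 50% passing.** Expected fall = (1 - r) x SD x 0.798. With r = 0.6 and SD = 2.5: 0.4 x 2.5 x 0.798 = 0.80. With r = 0.8 and SD = 2.0: 0.2 x 2.0 x 0.798 = 0.32. Both are close to the simulated limits; the formula ignores rounding to whole points.

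**Falls of 2 or more points at 79% passing.** From Visit 1, 14-29%; from Visit 2, 12-24%. Most such falls are measurement noise, which a second baseline does not remove.

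**The Section 6.1.2.1 contrast.** That section does not define success at the end of sham; it is read here as a 2-point fall from Visit 1. At 79% passing, SD 2.5 and r = 0.7, with no true change:

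- sham falls of 2 or more points from Visit 1: 25%
- the same from Visit 2: 21%
- Trial Stage success under the plan's rule: 11.5%

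The gap is 25 - 11.5 = 13.5 percentage points. Selection accounts for 25 - 21 = 4 of them (4/13.5 = 30%). The other 9.5 come from the lower-of-two reference.

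**False significance.** If the Wilcoxon test is applied to the Visit 1 to Visit 4 change in 45 subjects, a paired normal approximation gives the chance of a significant fall as Phi(mean / (SD of change / sqrt 45) - 1.96), nominally 2.5%. With about 89% passing (mean 0.129, SD of change 1.535): 0.129/0.229 = 0.56, so about 8%. With about 73% passing (0.354 and 1.853): 0.354/0.276 = 1.28, so about 25%.

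**Timing.** Consent precedes Visit 1 data, so the Visit 1 score is at most 30 days before placement. Visit 1 to Visit 4 then spans at most 30 + 21 = 51 days, of which up to 30 (59%) precede the device.

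**The case against.** **The primary endpoint is protected.** This stands. A chance high Visit 1 score does not create a Trial Stage success, because the reference is the lower of Visit 1 and Visit 4. A reader might infer that the success rate is inflated; the rule works the other way.

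**Selection is not the main source of imbalance in Section 6.1.2.1.** This also stands. A reader might suppose that stimulation success is measured from Visit 4, so that a clean sham baseline would level the comparison. The plan does not measure it that way, and in the worked scenario the lower-of-two rule causes more than two thirds of the gap.

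**The size may be small.** A reader might take 90 evaluated and 45 treated to mean that half fail the pain cut-off. Table 3 does not say so: "evaluation of minimum pain score on BPI3 inclusion criterion" is listed with INR and pregnancy testing, MMSE is also tested after consent, and 45 is an upper limit. Candidates are screened before consent and must have failed or not tolerated at least two therapies. Half failing on BPI3 is the extreme.

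**The gap before placement may be short.** A reader might conclude that the sham change covers seven weeks. The 30 days applies to the consent form, and the visit windows in Table 7 are redacted. It is a ceiling, not a schedule. Regression to the mean does not depend on it.

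**The pilot seeks only an indication of placebo effect** (Section 4.3.2). That lowers the stakes, but the error has a known direction and is cheap to remove.

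The absence of a Visit 2 BPI3 rests on the readable visit and endpoint text: Table 5 is broken in extraction and Section 4.5.2.1 is partly redacted.

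**Conclusion.** The point holds for the placebo estimate. One Visit 1 reading serves as both entry screen and start point, so the reported placebo effect includes regression to the mean, which overstates it, and any drift before placement, whose direction is unknown. Under the stated SD and correlation assumptions, the regression part is likely to be a few tenths of a point or less unless a large share of candidates fail the cut-off. It adds to any real sham response and does not replace it. In the sham-versus-stimulation contrast it works against the device but is the smaller part of the asymmetry. This is a low-cost improvement to a stated objective, not a threat to the primary analysis.

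**What to change.** Collect BPI3 at Visit 2 before lead placement. Leave unchanged the eligibility rule, the per-subject placebo labels that feed the success rules (Table 9), and the primary reference.

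In Sections 5.4.1.1 and 6.1.2.1:

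- Add the group-level sham-period change and the proportion with a 2-point fall from Visit 2 to Visit 4, beside the Visit 1 to Visit 4 figures.
- Set these against the like-for-like Visit 4 to Visit 5 change and 2-point falls, not only against the lower-of-two success rate. Without this step most of the asymmetry remains.
- For subjects without a Visit 2 score, report Visit 1 to Visit 4 as 'change from screening (placebo, regression to the mean and natural course combined)'.

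The cost is one question at an existing visit and a few lines of analysis. There are two downsides. Section 4.3.1 shows that data had already been collected, so subjects treated before the amendment will lack the score. And BPI3 asks about the past week, so the correction is only partial if Visit 2 falls within a week of Visit 1. Keeping the new figures at group level avoids giving a subject two conflicting placebo labels.

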**$P_0$  = BPI pain score at Baseline**

**$P_1$  = BPI pain score at End of Sham**

Then, a positive placebo effect is present in any subject who has a decrease in their BPI3 score from Baseline to the End of Sham:

**$P_1 < P_0$**

Alternatively, a negative placebo effect is present in any subject who has an increase in their BPI3 score from Baseline to the End of Sham:

**$P_1 > P_0$**

There is no placebo effect observed if a subject does not have a change in their BPI3 score from Baseline to the End of Sham:

**$P_1 = P_0$**

#### **5.4.1.2 Determination of SPR Trial Stage Success**

To determine if a subject is a Trial Stage Success, the BPI3 will be collected at the conclusion of the 6-week SPR Trial Stage. For each subject, the BPI3 score reported at the End of Trial Stim (Visit 5) will be compared to the BPI3 score reported at the End of Sham (Visit 4).

If

**$P_0$ =BPI pain score at Baseline**

**$P_1$ =BPI pain score at End of Sham**

#### **P2=BPI pain score at End of Trial Stim**

Then, subjects who demonstrate a positive placebo effect (or no placebo effect) will be considered SPR Trial Stage successes if they demonstrate a 2-point or greater decrease in their BPI3 score from the End of Sham to the End of Trial Stim:

$$P_1 - P_2 \geq 2$$

If the BPI3 score at End of Sham (P1) is less than 2 (e.g. the value is 1 or 0), then BPI3 at the End of Trial Stage (P2) must equal 0 to be considered a Trial Stage Success.

Alternatively, subjects who demonstrate a negative placebo effect (as evidenced by an increase in the BPI3 score during the sham period) will be compared to Baseline (Visit 1), rather than End of Sham. It is critical to compare to the Baseline BPI3 score for these subjects, to ensure that they have achieved pain reduction as a result of the stimulation therapy and not as a result of a placebo effect.

For these subjects, they will be considered SPR Trial Stage successes if they demonstrate a 2-point or greater decrease in their BPI3 score from Baseline to the End of Trial Stim:

$$P_0 - P_2 \geq 2$$

#### **5.4.1.3 Determination of return of pain after Trial Stage**

To determine if a subject is eligible to advance from the SPR Trial Stage to the SPR Implant Stage, the BPI3 will be collected at least monthly for up to 6 months following Visit 5 (the end of Trial Stage stimulation) for those subjects who are Trial Stage successes. For each subject, the BPI3 score reported at the phone call will be compared to the BPI3 score reported at the End of Trial Stim (Visit 5).

If

**P2=BPI pain score at End of Trial Stim**

**P3=BPI pain score at phone call**

Then, subjects will be eligible to be screened for the Implant Stage if they demonstrate a sustained 2-point or greater increase in their BPI3 score from End of Trial Stim and their new BPI3 score is at least a 4:

$$P_3 - P_2 \geq 2 \text{ (sustained for two consecutive weeks)}$$
$$P_3 \geq 4 \text{ (sustained for two consecutive weeks)}$$

#### **5.4.1.4 Determination of SPR Implant Stage Success**

Implant Stage subject success will be determined by comparing their BPI3 score collected at 12-weeks IPG Stim ON (Visit 10) to the End of Sham BPI3 score (Visit 4).

If

**$P_0$ =BPI pain score at Baseline**  
 **$P_1$ =BPI pain score at End of Sham**  
 **$P_2$ =BPI pain score at End of Trial Stim**  
 **$P_4$ =BPI pain score at 12-weeks IPG Stim ON**

Then, subjects demonstrating a positive placebo effect (or no placebo effect) will be considered an Implant Stage success if they demonstrate a 2-point or greater decrease in their BPI3 score from End of Sham to 12-weeks of IPG stimulation therapy:

$$P_1 - P_4 \geq 2$$

As with the determination for pain relief in the SPR Trial Stage, subjects who demonstrate a negative placebo effect (increase in the BPI3 score after End of Sham) will have their BPI3 score at 12-weeks of IPG stimulation therapy (Visit 10) be compared to their score at Baseline (Visit 1).

For these subjects, they will be considered an Implant Stage success if they demonstrate a 2-point or greater decrease in their BPI3 score from Baseline to 12-weeks of IPG stimulation therapy:

$$P_0 - P_4 \geq 2$$

#### 5.4.1.5 Summary of Pain Score Comparisons

Table 9 summarizes the comparisons that are necessary to determine whether or not a placebo effect is present in each subject, if a subject is a Trial Stage Success, if the subject is eligible to advance to the SPR Implant Stage, and if a subject is considered an Implant Stage success.

**Table 9.** Summary of Pain Score Comparisons

Baseline BPI3	End of Sham BPI3*	Result of Comparison of Sham vs. Baseline	Placebo Effect	End of Trial Stage BPI3*	Trial Stage Success Criteria	Criteria to be consented/screened for the Implant Stage	12-weeks IPG Stim ON	Implant Stage Success Criteria
$P_0$	$P_1$	$P_1 < P_0$	Positive placebo effect	$P_2$	$P_1 - P_2 \geq 2$	$P_3 - P_2 \geq 2$ $P_3 \geq 4$	$P_4$	$P_1 - P_4 \geq 2$
$P_0$	$P_1$	$P_1 = P_0$	No placebo	$P_2$	$P_1 - P_2 \geq 2$	$P_3 - P_2 \geq 2$ $P_3 \geq 4$	$P_4$	$P_1 - P_4 \geq 2$

$P_0$	$P_1$	$P_1 > P_0$	Negative placebo effect	$P_2$	$P_0 - P_2 \geq 2$	$P_3 - P_2 \geq 2$ $P_3 \geq 4$	$P_4$	$P_0 - P_4 \geq 2$
-------	-------	-------------	-------------------------	-------	--------------------	------------------------------------	-------	--------------------

\*If the BPI3 score at End of Sham ( $P_1$ ) is less than 2 (e.g. the value is 1 or 0), then BPI3 at the End of Trial Stage ( $P_2$ ) must equal 0 to be considered a Trial Stage success.

